8.3 Analyses prior to the end of the study

Blinded analyses of pharmacokinetics and serum neutralization may be performed after all subjects in a particular group complete the final study visit. An unblinded analysis may be performed by an unblinded statistician. These analyses will allow a more rapid assessment to facilitate program development. Blinding of study staff will be maintained.

9 Data and Sample Storage

The Principal Investigator will oversee how the data are collected, entered, and protected. All study data will be collected by the clinical study staff using designated source documents and entered onto the appropriate electronic case report forms (eCRFs). Data collection forms (DCFs) will be provided by Emmes for use as source documents as appropriate. All study data must be verifiable to the source documentation. All source documents will be kept in a locked facility at the clinical site and remain separate from participant identification information (name, address, etc.) to ensure confidentiality. All medical records (when not being reviewed by the research team) will be kept under lock and key in the Medical Record Department of the hospital with access limited to the appropriate RUH personnel, members of the RUH-IRB and the FDA. Source documentation will be available for review to ensure that the collected data are consistent with the eCRFs.

All eCRFs and laboratory reports will be reviewed by the clinical team, who will ensure that they are accurate and complete.

All research samples will have a unique identifier. The PI will be responsible for ensuring project compliance, data analysis and entry, regulatory monitoring, and coordination of the activities of the entire study team. Standard GCP practices will be followed to ensure accurate, reliable and consistent data collection.

Source documents include, but are not limited to:

- Signed Informed Consent Documents
- Dates of visits including dates of infusion
- Documentation of any existing conditions or past conditions relevant to eligibility
- Reported laboratory results
- All adverse events
- Concomitant medications
- Reactogenicity adverse events

The PI and sponsor (Rockefeller University) are the owners of the data. The PI will take primary responsibility for the data. Data will first be collected on paper charts and then transferred into a secure online database managed by the Emmes Corporation. Access to the Emmes website is granted only after an authorized individual (e.g., PI, Study Coordinator or supervising monitor at Rockefeller University) grants permission and a staff member completes a roster form stating his or her study role/responsibilities and contact information. Access to the data system requires a different username and password from the Emmes website, and access can be tailored based on the user's role/ responsibilities in the study. The only protected health information entered into the Emmes database is participants' DOB. This is done in order to confirm that a participant meets age-eligibility criteria. DOB is then converted to age and does not appear on any data summaries sent from Emmes. All Emmes websites use SSL for secure transport. The clinical study team will have access to the Emmes database, however, only a single study team member will input data into the database. Changes to the database are tracked by user and time of entry. Password-protected data summaries that contain no protected health information are released to the PI from Emmes through ELF and will be secured on the PI's encrypted password protected computer. Study team members may also store these data summaries on their own encrypted password-protected computers.

De-identified blood samples will be sent to a collaborator at Beth Israel Deaconess and the resulting data will be returned by email to the PI. The Exchange email system will be used by our collaborator to report the result of the assay. These reports contain no protected health information.

10 Recruitment and Advertising

Both men and women ages 18 through 65 will be recruited for the study from the community at large and will be referred by physicians in the community. We will make every effort to recruit minorities and women.

We project screening 72 participants in order to achieve at least 24 evaluable participants. In case of drop-outs an over-enrollment of 10% (2 participants) will be allowed.

Advertisements – The RUH Clinical Research Support Office (CRSO) will utilize the Volunteer Repository. Advertisements will also be placed: online (e.g. Craiglist, Centerwatch, etc), in newspapers (Metro, AMNY) and on campus.

The Research Match tool will also be utilized.

Centralized Call Management – The RUH CRSO will conduct telephone screenings of selected Volunteer Repository members, and of volunteers who call [name], to facilitate screening efficiently. Based on IRB approved eligibility criteria, potentially eligible candidates pre-screened by CRSO staff will be referred to the study coordinator/investigator for further evaluation. The research team and CRSO will work together on a protocol-specific pre-screening script to optimize the process.

11 Potential Benefits to Participants

There are no direct benefits to participants that enroll in this study.

12 Potential risks to the participant

This study entails moderate risk to participants since 3BNC117 and 10-1074 are investigational products with limited safety data in humans. This is the first time that both antibodies will be administered in combination and the first time that 3 doses of 10-1074 will be administered. Potential study participants will be informed about the possible risks associated with 3BNC117 and 10-1074 infusions and that there may be unknown risks.

Potential risks associated with the combination of 3BNC117 and 10-1074:

While each mAb product has unique safety issues related to its mechanism of action, the major safety concern related to mAbs in general is an infusion/hypersensitivity reaction. These types of reactions are more common for mAbs that contain murine elements compared to human mAbs, such as 3BCN117 and 10-1074. Passive administration of anti-HIV-1 antibodies has been evaluated in humans in the past. As observed with other monoclonal antibodies, anti-HIV-1 antibodies, including 3BNC117 and 10-1074 have been found to be generally safe and well tolerated and most adverse events observed were transient myalgia, fatigue and headache.

3BNC117 and 10-1074 have not been administered together in the past. However earlier generation anti-HIV antibodies (2F5, 4E10, 2G12) were administered intravenously in combination at doses ranging from 1 to 2 g per infusion of each antibody (or 12.5 to 25 mg.kg, assuming 80 kg body weight); 13-16 weekly antibody infusions were given (Trkola, Kuster et al. 2005) (Mehandru, Vcelar et al. 2007). In these two studies, antibody infusions were well tolerated and reported side effects were mild and transient. Most commonly reported adverse events were fatigue, body aches, arthralgia, and low-back ache. No serious adverse events (SAEs) were recorded. In addition, in a GLP-study, rats were administered 4 weekly doses of 3BNC17 and 10-1074 at 60 mg/kg. Based on the results of this study, and absence of apparent direct toxicity of the test item in the presence of apparent immunogenicity, the No-Observed-Adverse-Effect-Level (NOAEL) of the combination intravenous dose of 10-1074 and 3BNC117 in rats was considered to be 60 mg/kg/injection, each administered once weekly, for up to 25 days. Although unlikely, it is possible that the combination of 3BNC117 and 10-1074 will lead to a higher frequency of adverse events and/or to adverse events of higher severity than either antibody administered alone

- Immunologic symptoms such as listed below are possible with administration of a monoclonal antibody and will be considered adverse events of interest. Potential allergic-type reactions during and immediately following the administration of the antibodies will be carefully monitored.
 - Constitutional symptoms, such as fever, rigors/chills;
 - Infusion site reaction/extravasation changes, pruritus, urticaria;
 - Serum sickness like syndromes as evidenced by fever, rash, arthralgia, arthritis, nephritis;
 - Deposition of immune complexes in the kidneys leading to renal insufficiency;
 - Adult Respiratory Distress Syndrome, bronchospasm/wheezing, anaphylaxis;
 - Cytokine release syndrome/ acute infusion reaction.
- In the cross-reactivity study in human tissues, 3BNC117 stained rare cells in the conjunctival recesses. When rats were administered 3BNC117, ocular toxicity was not observed. Sixty-eight participants have received 3BNC117 to date, and 12 participants reported mild ophthalmic complaints (such as pruritus, conjunctival erythema, increased lacrimation) during study follow up. In all instances symptoms resolved without specific treatment and ophthalmologic evaluations 5 months after 3BNC117 administration did not show changes from baseline.
- In the cross-reactivity study in human tissues, 10-1074 stained the cytoplasm of nerve cells in the optic nerve of the eye. Twenty-two participants have received 10-1074 to date. One participant reported transient and mild dryness in the eyes.
- Participants might have false positive HIV serology results after 3BNC117 and 10-1074 administration. This will likely be temporary, while antibody levels are detectable in blood.
- The adverse effects of 3BNC117 and 10-1074 to a fetus or unborn child are unknown.

Other potential risks

- Blood drawing and phlebotomy can be associated with pain, bruising, anemia or infection at the site of venipuncture. Rarely, fainting may follow phlebotomy.
- Participants may engage in increased risk taking after receiving anti-HIV mAb infusion. One to one counseling will be routinely performed.

12.1 Procedures to minimize risk

- As outlined above, this study will be an exploratory phase 1 trial of the combination of 3BNC117 and 10-1074. Potential study participants will be informed about possible risks of the monoclonal antibody and that there may be unknown risks.
- Medical records and routine laboratory data will be handled with HIPAA compliance and protected by the rules and regulations of the RUH, a JCAHO approved institution.
- Following enrollment in Group 1, enrollment in subsequent group will only begin following a review of Day 28 safety data from all participants in the prior group.
- To minimize risks associated with phlebotomy, blood drawing will be performed by experienced phlebotomists.
- To minimize risks associated with blood drawing, participants will be closely monitored for signs and symptoms of anemia.
- Females of childbearing potential and who participate in sexual activity that might lead to pregnancy will be advised to use two reliable forms of contraception (i.e. condom with spermicide, diaphragm with spermicide, hormone-eluting IUD, hormone-based contraceptive with condom) for the duration of the study. In addition, a pregnancy test will be performed at screening, on the day of each drug infusion, and other times throughout the course of the study. Males who are not anatomically sterile and who participate in sexual activity that might lead to pregnancy will be advised to use two reliable forms of contraception from 10 days prior to the 3BNC117/10-1074 infusion until the end of the study to avoid pregnancy in a spouse or partner. Condoms will be provided.
- Participants will have regularly scheduled visits to the outpatient clinic and routine safety laboratories will be checked according to the Time of Events Schedule (Appendix A).
- Adverse events will be monitored and graded using the Toxicity Grading Scale for Healthy Adult and Adolescent Volunteers Enrolled in Preventive Vaccine Clinical Trials (HIV-uninfected). The CTCAE v4.03 grading scale will be used for reporting

and grading adverse events related to infusion reactions and cytokine release syndromes in all groups (Appendix B).

- Adverse events will be managed by the clinical trial team who will assess and treat the event as appropriate, including referral to an independent physician and/or department.
- Safety monitoring will be conducted by the study investigators, by an external Study Monitoring Committee (SMC), and by the International AIDS Vaccine Initiative (IAVI). The RUH-IRB will conduct the initial review of the proposed study and will follow progress through annual reports and by immediate notification of serious adverse events. Any serious and unanticipated adverse events will be immediately reviewed by the study investigators. Investigators will notify the RUH-IRB within 2 working days from the investigators being made aware of the event. The RU sponsor will notify the FDA, per 21 CFR 312. The SMC will be available to the investigators for consultation and review of severe adverse events if needed.

13 Data and Safety Monitoring Plan

This is a phase 1 study, which exposes study participants to "moderate risk". A Study Monitoring Committee (SMC) will be established to monitor the study.

1. If > 1 grade 3 or higher adverse events deemed probably or definitely related to the study drugs occur in a single group, no additional administration of the investigational product will take place pending a Safety Monitoring Committee (SMC) review. The SMC will provide a recommendation regarding subsequent enrollment in the study.

2. If there is one SAE judged as possibly, probably or definitely related to the administration of 3BNC117 and/or 10-1074 by the principal investigator or designee, no additional administration of the investigational product will take place pending a review by at least two members of the SMC. Following this review, the SMC will make a recommendation to the principal investigator regarding the continuation of investigational product administration.

SAEs, which are deemed possibly, probably or definitely related to 3BNC117 and/or 10-1074 by the principal investigator or designee, and unanticipated adverse events will be reported to the SMC within 2 working days of the site becoming aware of the event.

3. If, at any time, a fatal, life-threatening or permanently disabling SAE with a suspected causal relationship to 3BNC117 and/or 10-1074 occurs, no further administration of the

investigational products will occur until a consensus plan forward has been approved by investigators, SMC, the IRB, and the FDA.

4. The SMC will be informed within 2 working days of any participant who discontinues study treatments as a result of a grade 2 ophthalmologic adverse event deemed related to the study products or a grade 3 or 4 ophthalmologic adverse event deemed unrelated to the study drugs.

5. The SMC will be informed within 2 working days of any participant who discontinues receipt of the study products as a result of liver test abnormalities as described in Section 6.1.7.2.

6. In addition, the SMC will be asked to review on an interim basis:

- Severe solicited and unsolicited adverse events judged by the principal investigator or designee to be possibly, probably or definitely related to 3BNC117 and/or 10-1074.

- Severe laboratory adverse events confirmed on retest and judged by the principal investigator or designee to be possibly, probably or definitely related to 3BNC117 and/or 10-1074.

The occurrence of such adverse events will not result in a study pause, unless it is judged by the principal investigator or designee that the risk/benefit ratio of the study has changed such that risk of currently enrolled or future participants has increased; or unless recommended by the IRB, SMC, or FDA.

All updated versions of the protocol will be provided to the SMC. Review of unblinded trial data by the SMC will take place at least annually. Prior to data review, the study team will provide the SMC with updated records of all adverse events (AEs) of a grade 2 or higher.

The SMC will acknowledge receipt of annual reports and will indicate if there are concerns with the continuation of the study.

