6.1.4 Post-3BNC117/10-1074 Administration Visits

Participants will be followed for 24 weeks after the last 3BNC117 and 10-1074 infusions.

At these follow up visits the following will be conducted:

- Review of interim medical history and use of concomitant medications;
- If symptoms are present, perform a symptom-directed physical examination;
- Local and systemic reactogenicity adverse events, as well as other adverse events, will be assessed;
- Pregnancy and safe sex counseling;
- Vital Signs;
- Collect blood and urine specimens for all tests as indicated in the Time of Events Schedule (Appendix A);
- In case of adverse event(s), the participant will be assessed and followed up by the clinical team. Supplemental visit(s) for further investigation can be planned at the discretion of the principal investigator or designee. Supplemental visit(s) may be recommended if clinically indicated or to clarify observations.
- Any participant that develops signs or symptoms of ocular disease will be promptly referred to an ophthalmologist for diagnosis and management
- Participants in Group 1 will have scheduled ophthalmologic exams at Day 28; participants in Groups 2 and 3 will have a scheduled ophthalmologic exam at Week 20 (28 days following the third dose).

Specific procedures to be performed at each follow up visit for Groups 1, 2, and 3 are illustrated in the Time of Events Schedules (**Appendix A**).

Any abnormalities (adverse events) attributed to study drug, including laboratory abnormalities, should be subsequently followed until the event or its sequelae resolve or stabilize.

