6.1.7.2 Discontinuation from subsequent 3BNC117/10-1074 infusions

Participants will be discontinued from second or third 3BNC117/10-1074 infusions for any of the following reasons:

- 1. A disease or condition or an adverse event that may develop, regardless of relationship to 3BNC117 or 10-1074, if the principal investigator or designee is of the opinion that other 3BNC117 or 10-1074 infusions will jeopardize the safety of the participant.
- 2. Any immediate hypersensitivity reaction (such as urticarial rash; bronchospasm; laryngeal edema; anaphylaxis; syncope).
- 3. Any grade 2 ophthalmologic adverse event deemed related to the study products, or any grade 3 or 4 ophthalmologic adverse event regardless of causality assessment.
- 4. Any ALT or AST increase equal to or greater than 3x the upper limit of normal with concurrent increase in total bilirubin equal to or greater than 2x the upper limit of normal. Additionally, such an occurrence will also result in a consultation with a hepatologist to assess for other evidence of drug toxicity.
- 5. Any participant with a graded elevation in total bilirubin will undergo a diagnostic workup at no cost to the participant that includes right upper quadrant ultrasound, testing for gamma glutamyl transferase (GGT), HAV, HBV, HCV, EBV serologies, CMV serologies, VZV serologies, HSV serologies, and any other relevant laboratory tests as determined by the investigators. Further administration of the investigational products will be discontinued for any participant with a grade 3 or above elevation in total bilirubin for whom this evaluation fails to determine the etiology.
- 6. Life threatening medical event following 3BNC117 and/or 10-1074 unless not related to the investigational product.
- 7. Intercurrent use of immunosuppressive medication considered significant by the trial physician (e.g., systemic corticosteroids).
- 8. Pregnancy.
- 9. Participant's request to discontinue further 3BNC117 or 10-1074 infusions.

- 10. A participant in Groups 2 or 3 who misses the second dose of mAbs or placebo will not receive the third dose.
- 11. Any participant who misses an infusion will not attend the Day +2 visit following the missed dose.

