7.1 Regimen

3BNC117 and 10-1074 will be administered intravenously at 3 or 10 mg/kg.

- Group 1: one infusion of 3BNC117 and 10-1074 at day 0, each dosed at 10 mg/kg.
- Group 2: three infusions of 3BNC117 and 10-1074, each dosed at 3 mg/kg, at day 0, weeks 8 and 16.
- Group 3: three infusions of 3BNC117 and 10-1074, each dosed at 10 mg/kg, at day 0, weeks 8 and 16.

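### The 2-working-day SMC notices for eye and liver events depend on a participant discontinuing infusions, so they cannot fire in Group 1, after the last infusion, or at any scheduled post-dose eye exam

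*Protocol*

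**What the plan says.** Section 13.1 of the protocol lists when the Safety Monitoring Committee (SMC) is told of or reviews events. Item 4 reads "The SMC will be informed within 2 working days of any participant who discontinues study treatments as a result of a grade 2 ophthalmologic" event deemed related, or a grade 3 or 4 eye event deemed unrelated. Item 5 gives the same notice for "any participant who discontinues receipt of the study products as a result of liver test abnormalities as described in Section 6.1.7.2".

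The criteria sit in section 6.1.7.2, which opens: "Participants will be discontinued from second or third 3BNC117/10-1074 infusions for any of the following reasons". Its eye criterion is "Any grade 2 ophthalmologic adverse event deemed related to the study products, or any grade 3 or 4 ophthalmologic adverse event regardless of causality assessment". Its main liver criterion begins "Any ALT or AST increase equal to or greater than 3x the upper limit of normal with concurrent increase in total bilirubin" to at least twice the upper limit; unexplained bilirubin elevation of grade 3 or above also counts.

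Under section 7.1, Group 1 receives "one infusion of 3BNC117 and 10-1074 at day 0, each dosed at 10 mg/kg". Group 2 receives "three infusions of 3BNC117 and 10-1074, each dosed at 3 mg/kg, at day 0, weeks 8 and 16", and Group 3 follows the same schedule at 10 mg/kg. Section 6.1.4 puts the scheduled post-dose eye exam at Day 28 in Group 1, while "participants in Groups 2 and 3 will have a scheduled ophthalmologic exam at Week 20 (28 days following the third dose"). Section 4 gives 24 weeks of follow-up after the final infusion.

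**The concern.** Items 4 and 5 single out eye and liver events for rapid notice to the independent committee, but they hang the notice on a consequence of the event (loss of a later infusion) and not on the event. Where no later infusion is planned, that consequence cannot occur. The same related grade 2 eye event is notifiable within 2 working days if it appears at Week 6 in Group 2, and not under this rule if it appears at Week 20 or anywhere in Group 1.

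Group 1 is where the combination is first given to people (section 12), and the scheduled eye exams are the visits meant to detect eye toxicity. These are the places where items 4 and 5 are silent. At stake is whether the SMC hears promptly of a class of event that the protocol itself chose for prompt notice.

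**Working it through.** No sample-size formula applies. The check is of rule logic, supported by counts.

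**1. Can a discontinuation under the eye or liver criteria occur?**
- Section 6.1.7.2 covers only the second or third infusion.
- Section 6.1.7.1, on stopping an infusion in progress, lists immediate hypersensitivity and life-threatening events. It has no eye-grade or liver-test criterion. A stop for an acute infusion reaction (section 6.1.3) is likewise not a stop under the 6.1.7.2 eye or liver criteria.
- Group 1 has no second infusion, so no discontinuation is possible. In Groups 2 and 3 none is possible after Week 16.

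**2. Is there an eye exam while an infusion remains?** Appendix A is not shown, so I checked section 6.1.4 against the payment totals in section 6.2.10. Those are $25 for screening, $200 per infusion visit, $80 per follow-up visit, $100 for the final visit and $50 per eye exam.
- Group 1: 1065 − 25 − 200 − 100 = 740. With 2 eye exams, 740 − 100 = 640 = 80 × 8 follow-up visits.
- Groups 2 and 3: 2105 − 25 − 600 − 100 = 1380. With 2 eye exams, 1380 − 100 = 1280 = 80 × 16 follow-up visits.
- Among 0 to 6 exams, only 2 gives a whole number of follow-up visits in either case. That fits one exam at screening (section 6.1.2) and one after dosing, with no mid-course exam.
- Scheduled post-dose exams: 8 at Day 28 and 16 at Week 20, 24 in all. Number with an infusion still to come: 0 of 24.

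**3. How much planned follow-up has an infusion still to come?** Inputs: 8 participants per group, last infusion at Week 0 (Group 1) or Week 16 (Groups 2 and 3), then 24 weeks.
- Group 1: 8 × 24 = 192 participant-weeks.
- Groups 2 and 3: 16 × (16 + 24) = 640. Total 832.
- Infusion still to come: 16 × 16 = 256; 256/832 = 30.8%. In Group 1: 0 of 192.
- No infusion to come: 24 × 24 = 576; 576/832 = 69.2%.

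**4. What do the other SMC routes cover?**

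| Route | Reaches the SMC | Leaves out |
|---|---|---|
| 13.1 item 2 and 13.4 | SAEs, within 2 working days | Non-serious events |
| 13.1 (under item 2) and 13.5 | Unanticipated events, within 2 working days; 13.5 limits this to related events above moderate severity | Events regarded as anticipated |
| 13.1 item 1 | More than one grade 3 or higher, probably or definitely related event in a group | Single events, grade 2, unrelated events |
| 13.1 item 6 | Severe related events, on an interim basis with no 2-day limit; laboratory events need a confirming retest | Related grade 2; unrelated grade 3–4 |
| 13.1, closing text | Records of grade 2 or higher events, before the at-least-annual review | Nothing by grade, but no early deadline |

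A related grade 2 eye event, or an unrelated non-serious grade 3–4 one, arising after the last infusion and regarded as anticipated, passes through every row except the last.

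**The case against.** The strongest reply is that items 4 and 5 report individual treatment stops, do that job as written, and sit among several other safeguards. Much of this stands.

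- **Unanticipated events.** Section 13.1 sends these to the SMC within 2 working days with no discontinuation condition. Section 12 lists no isolated liver risk, so a combined transaminase and bilirubin rise may well qualify. For the eye, section 12 describes only mild complaints (12 of 68 recipients of 3BNC117, one of 22 recipients of 10-1074), so a grade 2 finding could be argued to exceed the known risk. But the term is not defined, and 13.5 words its own rule more narrowly. The route is arguable, not assured.
- **Severity of liver events.** Whether a rise meeting the 6.1.7.2 criterion would be graded severe depends on Appendix B, which is not shown. A liver hole in item 6 for related events is therefore not established.
- **The Day 28 gate.** A reader might infer that a Group 1 eye finding goes unexamined before Group 2 opens. It does not: section 4 requires Day 28 data including eye exams, and section 12.1 requires a review of them. That review is not assigned to the SMC, however, and the stated hold needs more than one grade 3 or higher event judged probably or definitely related.
- **Annual review.** A reader might also infer that such an event reaches the SMC only once a year. The protocol says at least annually, which is a minimum. It also provides a medical monitor, at-least-quarterly external monitoring and SMC consultation on severe events.

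It is also true that the protocol nowhere promises 2-day notice of every eye or liver event, so this is not a contradiction. But it gives no reason why the same event should be notifiable before Week 16 and not at the exam scheduled to find it.

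**Conclusion.** The point holds in limited form. As worded, items 4 and 5 cannot fire in Group 1, after Week 16 in Groups 2 and 3, or at any of the 24 scheduled post-dose eye exams. They can operate in at most 31% of planned participant-weeks.

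The 69% is time without a remaining infusion. It should not be read as a share of events missed, because the other routes run throughout. The gap that survives is mainly a non-serious, arguably anticipated eye event after the last infusion (related grade 2, or unrelated grade 3–4), which has no required SMC route before the at-least-annual review. The liver gap is possible but less certain.

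This assumes 24 participants completing the planned schedule, and eye-exam timing as in section 6.1.4, which the payment totals support in the absence of Appendix A. It is a cheap improvement to safety oversight, not a failure of SMC reporting as a whole.

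**What to change.** In section 13.1, items 4 and 5, make the event the trigger: inform the SMC within 2 working days of the site becoming aware of any participant whose eye event or liver result meets the section 6.1.7.2 criterion, at any time after any infusion and whether or not further infusions are planned. Leave the discontinuation criteria as they are; only reporting changes.

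Coverage by these two items would rise from 256 to all 832 planned participant-weeks, and from 0 to 24 of the 24 scheduled post-dose eye exams. Pointing item 4 to the 6.1.7.2 criterion also brings in related grade 3–4 eye events, which item 4 does not now list and item 6 covers without a deadline. The cost is a wording change in two items and a few extra notices to the SMC in a 24-participant trial.
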